3.6.1.1 Other significant adverse events

During the evaluation of the AE data, a medically qualified expert will review the list of AEs that were not reported as serious AE (SAEs) or AEs leading to discontinuation.

Based on the expert's judgment, significant AEs of particular clinical importance may, after consultation with the AstraZeneca Global Patient Safety Physician, be considered other significant AEs (OAEs) and reported as such in the CSR.

Examples of these are marked haematological and other laboratory abnormalities, and certain events that led to intervention (other than those already classified as serious), dose reduction, or significant additional treatment.

3.6.1.2 Adverse events of special interest

Adverse events of special interest will be recorded as such in the eCRF. MACE events will be classified according to the assessments of the Cardiovascular Event Adjudication Committee. AESIs are defined as follows:

- Non-opportunistic serious infections
- Opportunistic infections
- Anaphylaxis
- Malignancy
- Herpes zoster
- Tuberculosis (TB), including latent TB (LTB)
- Influenza
- Vasculitis (non-SLE)
- MACE (as adjudicated)

AESIs are further defined in the clinical study protocol. An AESI that meets one of the seriousness outcomes listed in Section 6.2 of the clinical study protocol will also be categorised as an SAE.

3.6.2 Laboratory variables

Parameters of haematology, clinical chemistry, urinalysis (outlined in Table 4, Section 5.4 of the clinical study protocol) and of fasting lipid profile (high density lipoprotein cholesterol, low density lipoprotein cholesterol, and triglycerides) will be examined.

Laboratory data will be reported in SI units. Changes from baseline in haematology, clinical chemistry and lipid profile variables will be calculated.

Absolute values will be compared to the reference range as given in [Appendix F](#) and classified as low (below range), normal (within range or on limits) or high (above range). All values (absolute and change) falling outside the reference ranges will be flagged.

Treatment emergent laboratory/vital signs changes (TELVC) will be defined for on-treatment values according to the reference ranges given in [Appendix F](#).

Urinalysis data that is continuous will be reported and summarised as for haematology and clinical chemistry data. Categorical urinalysis data will be categorised as negative (0), trace (trace), or positive (+, ++, +++, or >+++) at each time-point. Treatment-emergent changes will also be assessed. Treatment-emergent changes of urinalysis data are defined as

- Negative/+ at baseline to ++, +++, ++++ at any on-treatment value OR
- Increase of from baseline of at least ++ at any on-treatment value.

For the liver function tests: aspartate transaminase (AST), alanine transaminase (ALT), alkaline phosphatase (ALP), gamma glutamyl transferase (GGT) and total bilirubin, the multiple of the upper limit of the normal (ULN) range (see [Appendix F](#)) will be calculated for each data point as follows:

Multiple=Value/ULN (i.e. if the ALT value was 72 IU/L (ULN = 36) then the multiple would be 2)

Subjects meeting any of the following biochemical criteria for Hy's law (potential Hy's Law) at any point during the study will be flagged:

- $AST \geq 3x \text{ ULN}$
- $ALT \geq 3x \text{ ULN}$
- Total bilirubin $\geq 2x \text{ ULN}$

3.6.3 Electrocardiograms

A 12-lead ECG tracing will be performed locally at screening, Week 52 and Week 104. The Investigator or qualified designee will review the ECG for clinically significant acute changes. The following categories used for analysis:

- Normal,
- Abnormal, not clinically significant
- Abnormal, clinically significant.

The number of subjects in each category will be presented.

3.6.4 SLEDAI-2K-based flare assessment instrument

The SLEDAI-2K based Flare Assessment Instrument will be used to assess the extra-renal flares. Flares will be categorised as mild/moderate or severe and defined as any one criterion

in either the mild/moderate and/or severe flare categories. New or worsened manifestation should only be reported for manifestations of SLE. The distinction between mild and moderate flare will be based on investigators' judgement. The SLEDAI-2K based Flare Assessment Instrument consists of the following parts:

- Mild/moderate flare
 - Change in non-renal components of the SLEDAI-2K
 - New/worse manifestations of SLE
 - PGA
- Severe flare
 - Change in non-renal components of the SLEDAI-2K
 - New/worse manifestations of SLE
 - Hospitalisation
 - PGA

See Appendix M in the clinical study protocol for further details. Flares will be scored in comparison to the previous study visit (i.e. over the past 30 days) and will only include findings which, in the opinion of the investigator, are due to SLE disease activity within that timeframe.

3.6.5 Physical examination

Complete physical examinations will be performed and will include an assessment of the following components: general appearance, head and neck, skin, lymph nodes, thyroid, musculoskeletal/extremities, cardiovascular, respiratory, abdomen, neurological, genital/rectal and breast.

A focused physical examination will also be performed at specific on-treatment visits and this will include an assessment of the organ systems required to complete protocol-specified SLEDAI-2K assessment tool. Additional assessments will be done as clinically indicated. Abnormal findings will be recorded as part of medical history, AE, SAE, AESI, or lupus activity, as appropriate.

3.6.6 Vital signs

Vital signs will be obtained at each visit and measured several times around each infusion of IP as follows:

- Subjects will be monitored during the administration of the IP and for at least two hours after the first 4 infusions (Weeks 0, 4, 8, and 12). If there are no safety concerns, for subsequent infusions subjects will be monitored during administration of the IP and for a minimum of one hour after completion of the IV infusion thereafter (Week 16 to Week 100).
- Vital signs in a sitting position will be taken:

- Shortly before the infusion (up to 20 minutes before the beginning of the infusion)
- Every 15±5 minutes during infusion
- Immediately after completion of administration of IP, including post-dose saline flush (within 20 minutes after completion of the post-dose saline flush)
- Every 30±5 minutes after completion of IP administration (not including saline flush) for at least 2 hours after the first 3 doses (Week 0 to Week 8) of IP are administered, and for at least 1 hour, thereafter (Week 12 to 100)

Vital signs may also be taken more frequently if the investigator judges this to be appropriate.

The following vital signs will be examined:

- Pulse (beats per minute)
- Systolic blood pressure (mmHg)
- Diastolic blood pressure (mmHg)
- Respiration rate (breaths per minute)
- Body temperature (°C)

Changes from baseline will be calculated.

Where applicable, absolute values will be compared to the reference ranges given in [Appendix G](#) and classified as low (below range), normal (within range or on limits) or high (above range). All values (absolute and change) falling outside the reference ranges will be flagged.

On-treatment values will be classified as TELVC according to reference ranges given in [Appendix G](#).

Weight (kg) and BMI (kg/m²) will be measured at all study visits and examined using the difference in mean change from baseline longitudinally over time. BMI will be calculated at all visits using the associated visit weight measurement and the height measured at screening.

3.6.7 Cushingoid features

Subjects will be assessed for Cushingoid features such as moon face, buffalo hump, purple or violaceous striae, central obesity, hirsutism, acne, easy bruising, and fragile skin which will be captured separately within the study eCRF to evaluate whether resolution of same can occur overtime with OCS reduction. These features will be presented by visit.

3.6.8 Tuberculosis monitoring and questionnaire

Regular testing for TB/LTB will be assessed during the study. In addition, to aid in the early detection of new or reactivated TB, a TB questionnaire will be used to evaluate subjects for signs and symptoms of TB at every visit prior to receiving IP. Any confirmed incidence of TB/LTB will be recorded as an AESI (see Section [3.6.1.2](#)). All TB test results will be included as part of the laboratory outputs.

3.6.9 C-SSRS

The C-SSRS is an assessment tool that evaluates suicidal ideation and behaviour. It assesses the lethality of attempts and other features of ideation (frequency, duration, controllability, reasons for ideation, and deterrents), all of which are significantly predictive of completed suicide (see Appendix Q in the clinical study protocol for further details).

The following outcomes are C-SSRS categories and have binary responses (yes/no). The categories have been re-ordered from the actual scale in an increasing order of severity from 1 to 10 to facilitate the definitions of the comparative variables.

- Category 1 – Wish to be Dead
- Category 2 – Non-specific Active Suicidal Thoughts
- Category 3 – Active Suicidal Ideation with Any Methods (Not Plan) without Intent to Act
- Category 4 – Active Suicidal Ideation with Some Intent to Act, without Specific Plan
- Category 5 – Active Suicidal Ideation with Specific Plan and Intent
- Category 6 – Preparatory Acts or Behaviour
- Category 7 – Aborted Attempt
- Category 8 – Interrupted Attempt
- Category 9 – Actual Attempt (non-fatal)
- Category 10 – Completed Suicide

The Suicidal Ideation or Behaviour Score will be derived from the C-SSRS categories as the maximum suicidal ideation or behaviour category (1-10 on the C-SSRS) present at the assessment. The score will be derived at each assessment for each subject. Non-suicidal self-injurious behaviour will be assigned if no ideation or behaviour is present.

Composite variables based on the above re-ordered categories are defined for assessments during screening, during treatment, and during follow-up, respectively (with the same definitions for the study periods as given for AEs in Section 3.6.1), as follows:

Suicidal ideation: A “yes” answer at any time in the respective study period to any one of the 5 (re-ordered) suicidal ideation questions (Categories 1-5) on the C-SSRS.

Suicidal behaviour: A “yes” answer at any time in the respective study period, to any one of the 5 (re-ordered) suicidal behaviour questions (Categories 6-10) on the C-SSRS.

No suicidal ideation or behaviour: No “yes” answer at any time in the respective study period to any one of the 10 (re-ordered) suicidal ideation and behaviour questions (Categories 1-10) on the C-SSRS.

The total number of attempts, total number of interrupted attempts, and total number of aborted attempts will be derived for the different study periods by summing up all respective attempts during screening, during treatment and during follow-up, respectively.

Occurrence of suicidal behaviour and ideation, based on the C-SSRS, from baseline up to Week 52 will be presented.

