 - u This will be in addition to the central laboratory urinalysis. This will include urine sediment examination for red blood cells (RBC), white blood cells (WBC), and cellular casts (WBC, RBC and mixed) and hematuria on a dipstick test.
 - v Randomised subjects who receive anti-malarial therapy within 12 months prior to signing the ICF must have an eye exam by a qualified professional either within 12 months prior to signing the ICF or subjects who start on anti-malarial therapy during the Screening Period within 12 weeks after signing ICF.
 - w Check accountability and dispense Sponsor-provided MMF.
- 1 All Week 52 laboratory samples (blood and urine, including 24-hour UPCR sample) should be collected between Week 50 to Week 52, to allow assessment of PRR requirement for the second year participation.
 - 2 IP infusion at Week 52 is only for subjects who are continuing in second year extension period.

Table 3 Study plan detailing the procedures during follow-up (for subjects not participating in the second year extension period)

Study Period	Follow-Up Period	
	393±7 (8 weeks post final dose)	421±7 (12 weeks post final dose)
Days		
Visit Number	15 (Week 56)	16 (Week 60)
PtGA		X
C-SSRS (V1-V16)	X	X
PHQ-8		X
Vital signs	X	X
Tuberculosis Questionnaire	X	X
Physical examination	X	X
Weight	X	X
Blood collection for:		
Serum chemistry/haematology	X	X
Lupus serology tests (C3, C4, anti-ds DNA)	X	X
Type I IFN signature with 21-gene assay (PD marker)		X
RNA transcript profiling		X
ADA	X	X
PK blood samples ^a	X	X
Serum and plasma biomarkers		X
QFT-G test (TB testing), if applicable ^b		X

Study Period	Follow-Up Period	
Days	393±7 (8 weeks post final dose)	421±7 (12 weeks post final dose)
Visit Number	15 (Week 56)	16 (Week 60)
Urine collection for:		
Spot UPCR	X	X
Urinalysis (including microscopic examination) ^c	X	X
Local urinalysis (including microscopic examination) for selected sites ^d	X	X
Urinary biomarkers	X	X
Urine pregnancy tests (using dipstick)	X	X
eGFR using MDRD formula	X	X
SLEDAI-2K	X	X
PGA	X	X
AEs/SAEs/AESIs	X	X
SLEDAI-2K based Flare Assessment Instrument	X	X
Concomitant medications	X	X
Sponsor-provided MMF ^e	X	
Second renal biopsy (optional) ^f		X
Local clinical evaluation		X
Adjudication (optional)		X
Tissue biomarker ^g (optional)		X

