IP will be administered as an IV infusion via an infusion pump over no less than 60 minutes for the first 3 doses (Visit 1, 2 and 3). Starting with Visit 4, IP can be administered as an IV infusion via an infusion pump over no less than 30 minutes.

Randomisation will be stratified using two factors:

- Results of IFN test at screening using a 4-gene type I IFN test (IFN test-high versus IFN test-low)
- 24-hour UPCR ≤ 3.0 mg/mg versus >3.0 mg/mg (based on 24-hour UPCR performed on a sample obtained within 14 days prior to the expected date of randomisation). Without the results of the second (stratification) sample, subjects cannot be randomised. Turn-around time for results from central laboratory is up to 7 days.

On rare occasion an extension of the 30-day screening window may be allowed if re-collection of the 24-hour UPCR or other required samples is necessary or if the results needed for randomisation are delayed.

Renal biopsy performed within 12 weeks prior to signing the informed consent form (ICF) or during the screening period will be considered as the screening biopsy. Biopsies will be evaluated locally and the local classification will be used to confirm the eligibility criteria.

The biopsy must reveal Class III (\pm class V) or class IV (\pm class V) LN according to the World Health Organisation (WHO) or 2003 International Society of Nephrology/Renal Pathology Society (ISN/RPS) classification. An external renal biopsy adjudication group will adjudicate renal biopsies post-randomisation.

The overall study duration is approximately 116 weeks:

A Screening Period: Up to 30 days

Treatment Period:

The total treatment period is up to 100 weeks (26 doses administered Q4W).

- **52 week double-blind treatment period:** IP will be administered Q4W from Week 0 to Week 48 for a total of 13 doses. The primary endpoint will be evaluated at Week 52.
- **Second year extension period:** At Week 52, eligible subjects will continue treatment with randomised IP (anifrolumab 300 mg or placebo) administration Q4W from Week 52 to Week 100 for a total of 13 doses. The last efficacy assessments will be performed at Week 104.

Follow-up: After the completion of the last IP treatment (Week 48 for subjects who are not participating in the second year extension period and Week 100 for subjects who participate in the second year extension period) subjects will continue in the study for another 12 weeks of safety follow-up after the last administration of IP.

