3.6.1 Adverse events

Adverse events experienced by the subjects will be collected throughout the entire study, including the second year extension period, and will be coded using the latest version of MedDRA.

Adverse event data will be categorised according to their onset date into the following study periods:

- AEs occurring during screening:
An AE during screening is defined as an AE with a date of onset \geq date of the screening visit and date and time of onset $<$ date and time of the first dose of IP.
AEs occurring during screening will only be listed.
- AEs occurring during treatment:
An AE during treatment is defined as an AE with a date and time of onset \geq date and time of first dose of IP and \leq date of last dose of IP + 28 days.
- AEs occurring during follow-up:
An AE during follow-up is defined as an AE with a date of onset $>$ date of last dose of IP + 28 days and \leq date of last dose of IP + 84 days.
- AEs occurring after follow-up:
An AE after follow-up is defined as an AE with a date of onset $>$ date of last dose of IP + 84 days.
AEs occurring after follow-up will only be listed.

If an AE has a missing onset date, then unless the stop date of the AE indicates otherwise, this will be considered as an AE during treatment. Similarly, if an AE has a partial onset date, then unless the partial onset date or the stop date indicates otherwise, this will be considered an AE during treatment.

Adverse events with missing intensity will be assumed to be severe. Events with missing relationship to study medication per the investigator will be assumed to be related. If no information about seriousness is available, the AE will be considered serious.

An acute AE is defined as an AE with a date of onset on any day of administration of IP and a time of onset on or after the start of administration of IP or a date of onset occurring on the subsequent day. If an AE has a missing onset date, then unless the stop date of the AE indicates otherwise, this will be considered as an acute AE. Similarly, if an AE has a partial onset date, then unless the partial onset date or the stop date indicates otherwise, this will be considered acute AE.

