4.2.6.7 C-SSRS

The number and percentage of subjects with suicidal ideation (overall and by maximum category), suicidal behaviour (overall and by maximum category), and no suicidal ideation or behaviour will be presented by treatment group for assessments during screening, during treatment, and during follow-up, respectively.

Furthermore, descriptive statistics on the total number of attempts, total number of interrupted attempts and total number of aborted attempts will be summarised by treatment group for attempts during screening, during treatment and during follow-up, respectively.

Subjects with a suicidal ideation or behaviour at any time up until Week 52 will be presented in a listing.

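### C-SSRS assessments are placed in periods by the AE day limits, so some in-window Week 60 visits and later visits of early stoppers fall outside every C-SSRS period summary

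*SAP*

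**What the plan says.** SAP 3.6.9 defines its composite C-SSRS variables (ideation, behaviour, neither) and the attempt counts by screening, treatment and follow-up, "with the same definitions for the study periods as given for AEs in Section 3.6.1". In SAP 3.6.1 the treatment period runs up to and including "date of last dose of IP + 28 days". Follow-up runs from there to "date of last dose of IP + 84 days", inclusive. Anything later is after follow-up, and for AEs the consequence is stated: "AEs occurring after follow-up will only be listed".

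SAP 4.2.6.7 tabulates C-SSRS "for assessments during screening, during treatment, and during follow-up, respectively". There is no fourth column. The dedicated listing covers subjects with ideation or behaviour "at any time up until Week 52 will be presented in a listing", and the other presentation in SAP 3.6.9 runs from baseline to Week 52.

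The last dose is at "Week 48 for subjects who are not participating in the second year extension period" (SAP 1.2). For these subjects Protocol Table 3 schedules C-SSRS at Visits 15 and 16, and Visit 16 falls on Day "421±7 (12 weeks post final dose"). Table 4, for the extension, has no C-SSRS.

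Two statements point elsewhere. Protocol 8.4.5 and SAP 3.6 describe C-SSRS as a safety variable up to Week 52. SAP 3.6 also sets the default end of on-treatment C-SSRS values at the Week 52 visit.

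**The concern.** An AE has an onset date, so a day limit suits it. A C-SSRS assessment takes place at a visit and asks about the time since the previous one (Protocol 5.2.6), and the visit may move by a week in either direction. Here the day limits sit in the middle of two visit windows, so a day or two of ordinary scheduling decides the column.

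At Week 60, a late but compliant assessment leaves the three summarised periods altogether. The category for no ideation or behaviour is defined as the absence of any positive answer in the period. A subject whose only positive answer comes at such a visit is therefore reported as negative in follow-up.

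At Week 52, in subjects who do not enter Year 2, a late assessment is labelled follow-up although it reports on the interval since the Week 48 dose.

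The same rule also reaches subjects who stop IP early and, as Protocol 3.9.9 and 4.2.2 ask, keep attending to Week 52. Their visits more than 84 days after the last dose belong to no summarised period.

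**Working it through.** **Inputs.** Week 48 is Day 337, and Weeks 52, 56 and 60 are Days 365, 393 and 421 (Protocol Tables 2 and 3; SAP Table 2). The window is ±7 days, so each visit has 15 permitted days. Period limits are last dose + 28 and + 84 days (SAP 3.6.1).

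**Limits against visit days.** 337 + 28 = 365 = Week 52. 337 + 84 = 421 = Week 60. The second agrees with Table 3, which labels Day 421 as 12 weeks after the final dose.

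**Permitted days, dose on Day 337.**
- Week 52 (Days 358–372): Days 358–365 (8 of 15) are treatment; Days 366–372 (7 of 15) are follow-up.
- Week 56 (Days 386–400, i.e. + 49 to + 63): all 15 are follow-up.
- Week 60 (Days 414–428): Days 414–421 (8 of 15) are follow-up; Days 422–428 (7 of 15 = 46.7%) are in no summarised period.

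**From permitted days to a share of assessments.** This needs the distribution of actual visit days, which the documents do not give. Assumptions tried for Week 60:

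| Assumed timing | Share after + 84 days |
|---|---|
| Uniform over ±7, dose on Day 337 | 7/15 = 46.7% |
| Dose and visit independent, each uniform over ±7 | 105/225 = 46.7% |
| Bell-shaped, SD 2 to 5 days, dose fixed | 40% to 45% |
| Bell-shaped, SD 2 to 5 days, both vary | 43% to 46% |
| Bell-shaped, SD 1 day | 31% (dose fixed), 37% (both vary) |
| Share s exactly on the nominal day, rest symmetric: (1 − s)/2 | s = 30%, 50%, 70% gives 35%, 25%, 15% |

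The range is about 15% to 47%.

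**Early stoppers.** At nominal days a visit is beyond + 84 days when it is more than 12 weeks after the last dose. Visits up to Week 52 that fall outside:
- last dose Week 12: Weeks 28 to 52 (7 visits)
- last dose Week 24: Weeks 40 to 52 (4 visits)
- last dose Week 36: Week 52 only
- last dose Week 40 or 44: none

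**Would a limit of + 91 days do?** With the dose on Day 337, yes: the latest permitted Week 60 day is 428 = 337 + 91. If the dose may be 7 days early, the largest gap is 84 + 7 + 7 = 98 days. With both deviations uniform over ±7, the pairs with visit deviation minus dose deviation above 7 number 7 + 6 + 5 + 4 + 3 + 2 + 1 = 28, and 28/225 = 12% would still be excluded.

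**The case against.** **The Week 52 assessments are not lost.** This stands. One made later than + 28 days is still in a summarised period, and a positive answer appears in the baseline-to-Week-52 presentation and the listing. What remains is a wrong column label for non-continuers, at odds with the Week 52 on-treatment limit in SAP 3.6. The same outputs catch positives up to Week 52 in early stoppers, although the period table does not.

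**Records are not destroyed.** This also stands. SAP 4.1.3 provides for data listings, which may show late Week 60 records. SAEs are collected to the end of participation, and Protocol 5.2.6 requires referral irrespective of any table. The defect concerns the summary counts.

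**The SAP visit windows might rescue the visits.** SAP 4.1.1 assigns Days 407–434 to Week 60, but for visit-based analyses. The C-SSRS composites are defined by period, so the windows do not reach them.

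**The intention may be to stop C-SSRS at Week 52.** Two statements say so, yet Table 3 schedules Weeks 56 and 60 and SAP 4.2.6.7 plans a follow-up summary. This is a conflict to settle; it does not dispose of the point.

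**Stronger readings.** A reader might infer that nearly half of Week 60 assessments are lost. The documents support only 7 of 15 permitted days; the share of assessments is an assumption. A reader might also infer bias between arms. Entry to Year 2 depends on renal response at Week 52, so the number of subjects with a Week 60 C-SSRS may differ by arm. However, nothing links lateness by a few days to treatment in a double-blind trial, and neither direction nor size can be derived.

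**Conclusion.** The point holds as undercounting and misclassification in the C-SSRS period tables. It is exact that, for a dose on Day 337, 7 of the 15 permitted Week 60 days fall in no summarised period, and that no dedicated C-SSRS output picks those assessments up. Subjects positive only there count as negative in follow-up. It is also exact that 7 of the 15 permitted Week 52 days are labelled follow-up in non-continuers, and that early stoppers lose later visits from the period tables.

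The 15% to 47% range for Week 60 rests on assumed visit scatter. The number of affected subjects cannot be stated, because the documents do not give the numbers of non-continuers or early stoppers. The safety summaries are descriptive and no primary or secondary result is touched, but a suicidality count should not turn on a day's scheduling, and the correction is cheap. SAP 3.6.10, which assesses PHQ-8 by visit and includes Week 60, already shows the approach.

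**What to change.** Amend SAP 3.6.9 and 4.2.6.7 to assign C-SSRS by analysis visit and not by the AE day limits:

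- Subjects dosed through Week 48 who do not enter Year 2: post-dose visits through Week 52 are treatment; Weeks 56 and 60 are follow-up.
- Subjects who stop IP early: all C-SSRS visits after last dose + 28 days go in the follow-up (off-treatment) column, with no + 84-day cut-off.
- Use the same assignment for the counts of actual, interrupted and aborted attempts.
- Extend the listing of subjects with ideation or behaviour to Week 60.
- Reconcile the up-to-Week-52 statements in Protocol 8.4.5 and SAP 3.6 with Protocol Table 3 and SAP 4.2.6.7.

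Simply moving the limit to + 91 days is not adequate, because it still excludes some in-window visits when the last dose was early.

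The cost is a few sentences in the SAP, a change to the period derivation in programming, and aligned wording in the protocol. No new data or procedures are needed.
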